4.2 Exclusion Criteria

Potential participants are ineligible to enroll in the protocol if they:

1. Are not able to give adequate informed consent.
2. Are currently engaged in compensation litigation whereby financial gain would be achieved from prolonged symptoms of PTSD or any other psychiatric disorders.
3. Are likely, in the investigator's opinion and via observation during the Preparatory Period, to be re-exposed to their index trauma or other significant trauma, lack social support, or lack a stable living situation.
4. Have used Ecstasy (material represented as containing MDMA) more than 10 times within the last 10 years or at least once within 6 months of the first Experimental Session; or have previously participated in a MAPS-sponsored MDMA clinical trial.
5. Have any current problem which, in the opinion of the investigator or Medical Monitor, might interfere with participation.

Psychiatric History

6. Have received Electroconvulsive Therapy (ECT) within 12 weeks of enrollment.
7. Have a history of or a current primary psychotic disorder, bipolar disorder 1 assessed via MINI and clinical interview or dissociative identity disorder assessed via Dissociative Disorders Interview Schedule (DDIS) and clinical interview.
8. Have a current eating disorder with active purging assessed via MINI and clinical interview.
9. Have current major depressive disorder with psychotic features assessed via MINI.
10. Have a current moderate (not in early remission in the 3 months prior to enrollment; meets 5 of 11 diagnostic criteria per DSM-5) or severe alcohol or cannabis use disorder within the 12 months prior to enrollment (meets at least 6 of 11 diagnostic criteria per DSM-5).
11. Have an active illicit (other than cannabis) or prescription drug substance use disorder at any severity within 12 months prior to enrollment.
12. Have current Personality Disorders Cluster A (paranoid, schizoid, schizotypal), Cluster B (antisocial, borderline, histrionic, narcissistic), or Cluster C (avoidant, dependent, obsessive-compulsive) assessed via SCID-5-PD (Structured Clinical Interview for DSM-5 Personality Disorders).
13. Any participant presenting current serious suicide risk, as determined through psychiatric interview, responses to C-SSRS, and clinical judgment of the investigator will be excluded; however, history of suicide attempts is not an exclusion. Any participant who is likely to require hospitalization related to suicidal ideation and behavior, in the judgment of the investigator, will not be enrolled. Any participant presenting with the following on the Baseline C-SSRS will be excluded:
 - a. Suicidal ideation score of 4 or greater within the last month of the assessment at a frequency of once a week or more
 - b. Suicidal ideation score of 5 within the last 6 months of the assessment
 - c. Any suicidal behavior, including suicide attempts or preparatory acts, within the last 6 months of the assessment. Participants with non-suicidal self-injurious behavior may be included if approved by the Medical Monitor.
14. Would present a serious risk to others as established through clinical interview and contact with treating psychiatrist.
15. Require ongoing concomitant therapy with a psychiatric medication with exceptions described in [Section 12.0: Concomitant Medications](#).

Medical History

16. Have a history of any medical condition that could make receiving a sympathomimetic drug harmful because of increases in blood pressure and heart rate. This includes, but is not limited to, a history of myocardial infarction, cerebrovascular accident, or aneurysm. Participants with other mild, stable chronic medical problems may be enrolled if the site physician, CI, and Medical Monitor agree the condition would not significantly increase the risk of MDMA administration or be likely to produce significant symptoms during the study that could interfere with study participation or be confused with side effects of the IMP. Examples of stable medical conditions that could be allowed include, but are not limited to Diabetes Mellitus (Type 2), Human Immunodeficiency Virus (HIV) infection, Gastroesophageal Reflux Disease (GERD), etc. Any medical disorder judged by the investigator to significantly increase the risk of MDMA administration by any mechanism would require exclusion.

17. Have uncontrolled essential hypertension using the standard criteria of the American Heart Association (values of 140/90 milligrams of Mercury [mmHg] or higher assessed on three separate occasions).
18. Have a history of ventricular arrhythmia at any time, other than occasional premature ventricular contractions (PVCs) in the absence of ischemic heart disease.
19. Have Wolff-Parkinson-White syndrome or any other accessory pathway that has not been successfully eliminated by ablation.
20. Have a history of arrhythmia, other than occasional PVCs in the absence of ischemic heart disease, within 12 months of screening. Participants with a history of atrial fibrillation, atrial tachycardia, atrial flutter or paroxysmal supraventricular tachycardia or any other arrhythmia associated with a bypass tract may be enrolled only if they have been successfully treated with ablation and have not had recurrent arrhythmia for at least 1 year off all antiarrhythmic drugs, and confirmed by a cardiologist.
21. Have a marked Baseline prolongation of QT/QTc interval (e.g., repeated demonstration of a QTc interval >450 milliseconds [ms] in males and >460 ms in females corrected by Bazett's formula). For transgender or non-binary participants, QTc interval will be evaluated based on sex assigned at birth, unless the participant has been on hormonal treatment for 5 or more years.
22. Have a history of additional risk factors for *Torsade de pointes* (e.g., heart failure, hypokalemia, family history of Long QT Syndrome).
23. Require use of concomitant medications that prolong the QT/QTc interval during Experimental Sessions. Refer to [Section 12.0 Concomitant Medications](#).
24. Have symptomatic liver disease or have significant liver enzyme elevations.
25. Have history of hyponatremia or hyperthermia.
26. Weigh less than 48 kilograms (kg).
27. Are pregnant or nursing, or are of childbearing potential and are not practicing an effective means of birth control.
28. Have engaged in ketamine-assisted therapy or used ketamine within 12 weeks of enrollment.

4.3 Lifestyle Modifications

All participants must agree to the following lifestyle modifications at enrollment and throughout the duration of the study. Participants are eligible to enroll in the study if they:

- Are willing to commit to medication dosing, psychotherapy sessions, follow-up sessions, completing evaluation instruments, and all necessary telephone contact.
- Agree to not participate in any other interventional clinical trials during the duration of this study.

Leading up to Experimental Sessions

- Agree to take nothing by mouth except alcohol-free liquids after 12:00 A.M. (midnight) the evening before each Experimental Session.
- Refrain from the use of any psychoactive medication not approved by the research team from Baseline through Study Termination.
- Agree not to use caffeine or nicotine for 2 hours before and at least 6 hours after the initial dose during each Experimental Session.
- Are willing to comply with medication requirements per protocol (refer to [Section 12.0 Concomitant Medications](#)). Medications will only be discontinued after enrollment per clinical judgment of the site physician in consultation with the prescribing physician.

- Are able to decrease dose of allowable opiates (per [Section 12.0 Concomitant Medications](#)), if used for pain management, leading up to the Experimental Session in order to avoid taking the medication for at least 12 hours prior to the initial IMP administration and 24 hours after. During this period, the participant will be allowed to take the medication if needed for intolerable pain flare-ups.
- Agree that, for 1 week preceding each Experimental Session to refrain from:
 - Taking any herbal supplement (except with prior approval of the research team).
 - Taking any nonprescription medications (with the exception of non-steroidal anti-inflammatory medications or acetaminophen unless with prior approval of the research team).
 - Taking any prescription medications (with the exception of birth control, thyroid hormones, or other medications approved by the research team).

Post Experimental Session (for exceptions, see [Appendix A sub-study](#))

- Are willing to remain overnight at the study site after each Experimental Session until after the Integrative Session the next morning.
- Are willing to be driven home on the morning after the Experimental Sessions after the Integrative Session, either by a driver arranged by the participant, site personnel or taxi.

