12.2 Allowed Concomitant Medications

The site physician may prescribe necessary and appropriate medications in accordance with local and state regulations during the study to treat AEs that do not respond to other management outlined in the Treatment Manual. Examples include concomitant benzodiazepines for uncontrolled anxiety (for example, lorazepam at modest doses and occasional use only to avoid withdrawal effects of discontinuation between Experimental Sessions) or sleep aids (excluding trazodone) in compliance with [Section 12.3 Prohibited Medications](#). Sublingual nitroglycerin will be available on site in the case of emergency.

Gabapentin or certain opiates will be allowed when prescribed for pain management. The following opiates will be allowed during the study: hydrocodone, morphine, and codeine. Prior to randomization, participants who are taking opiates not included on this list will be cross-tapered to an allowable opiate under the care of their prescribing physician. Opiate medications may reduce the efficacy of MDMA and may prolong QT/QTc interval, but the opiates that are allowed during this trial have been selected because they have the lowest potential for QT/QTc interval prolongation and minimal serotonergic effects. Individuals using opiates for pain management will be asked to decrease the dose leading up to the Experimental Session in order to avoid withdrawal effects when they are required to refrain from taking the medication from 12 hours before IMP administration at the Experimental Session to 24 hours after. If a participant reports lack of analgesic effect during the sub-acute period following each Experimental Session, the site physician may approve taking an allowed opiate medication sooner than 24 hours after IMP administration.

If the participant is on stimulants for Attention Deficit/Hyperactivity Disorder (ADHD) at Baseline, they can continue to use them at the same dose and frequency, as long as they discontinue five half-lives before each Experimental Session and do not restart for 10 days after each Experimental Session.

All psychoactive medications, herbal supplements, nonprescription medications, and prescription medications must be reviewed by the research team at least 2 weeks prior to each Experimental Session. Failure to comply with protocol requirements for concomitant medications may result in withdrawal from treatment, depending on the investigator and Medical Monitor judgment.

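### Protocol Sections 4.3 and 12.2 set the same opiate-free interval around dosing but contradict each other on the exceptions and on who approves them

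*Protocol*

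**What the plan says.** Hydrocodone, morphine and codeine are allowed for pain, with a break around each dose.

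- **Protocol 4.3 (Lifestyle Modifications).** Participants must be able to lower their opiate dose before the session "in order to avoid taking the medication for at least 12 hours prior to the initial IMP administration and 24 hours after". The next sentence of the same bullet adds: "During this period, the participant will be allowed to take the medication if needed for intolerable pain flare-ups".
- **Protocol 12.2 (Allowed Concomitant Medications).** Over the same interval, "they are required to refrain from taking the medication from 12 hours before IMP administration at the Experimental Session to 24 hours after". The one relaxation reads: "If a participant reports lack of analgesic effect during the sub-acute period following each Experimental Session", then "the site physician may approve taking an allowed opiate medication sooner than 24 hours after IMP administration".
- **Consequence, also in 12.2.** "Failure to comply with protocol requirements for concomitant medications may result in withdrawal from treatment, depending on the investigator and Medical Monitor judgment".

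Section 12.3 repeats neither exception. On the dosing day, Protocol 8.3.1 has the site review concomitant medications, run a urine drug screen, and confirm that the participant has met the requirements of Section 4.3.

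**The concern.** The interval is identical in the two sections, so a site would expect the exceptions to be identical too. They differ in trigger, in timing and in approver. A participant who relies on the sentence in 4.3 can breach 12.2, and nothing states which text governs. Section 4.3 points to Section 12.0 for medication requirements in general, but it then grants its own explicit permission.

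Two things are at stake. First, drug exposure around dosing may be handled differently from site to site, in a trial whose protocol itself says that opiates may weaken the effect of MDMA. Second, the same act may be recorded as a deviation at one site and not at another. It may also lead to withdrawal from treatment at one and not at another.

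**Working it through.** The plan has no figure on this point to reproduce. The check sets the two texts side by side.

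**Interval.** Both sections start 12 h before the initial dose and end 24 h after it. With the 10:00 dosing time in Protocol Table 7:
- start: 10:00 − 12 h = 22:00 the evening before;
- end: 10:00 + 24 h = 10:00 the next day.

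**Exceptions.**

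| | Section 4.3 | Section 12.2 |
|---|---|---|
| Trigger | intolerable pain flare-up | lack of analgesic effect |
| When | anywhere in the interval | sub-acute period after the session |
| Approver | none named | site physician |

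**Cases.**

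| Opiate taken for an intolerable flare-up | 4.3 | 12.2 | Conflict |
|---|---|---|---|
| (a) in the 12 h before dosing | allowed | not allowed | yes |
| (b) in the 24 h after dosing, not approved | allowed | not allowed | yes |
| (c) in the sub-acute period after the session, approved by the site physician | allowed | allowed | no |

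**An example of (a) free of other rules.** Section 4.3 also restricts intake to alcohol-free liquids from midnight, and 8.3.1 requires a 10 h fast (10:00 − 10 h = 00:00). An opiate swallowed after midnight therefore raises a second question within 4.3 itself. An opiate at 23:00 does not. It falls before the fast and 11 h before a 10:00 dose, so it is inside the 12 h limit, permitted by 4.3 and barred by 12.2.

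**Route to the analysis.**
1. The dosing-day check in 8.3.1 names 4.3, so a site may record the participant as compliant.
2. Another site applying 12.2 may treat the same act as non-compliance, which can lead to withdrawal from treatment.
3. Under SAP 8.7.1, CAPS-5 data collected after treatment discontinuation are left out of the primary de jure analysis.
4. Even without withdrawal, the act may or may not appear in the deviation summary (SAP 8.3) and in the tabulation of excluded medications taken as deviations (SAP 8.8.3).

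**The case against.** The strongest reply is that the protocol already provides a decision route. Under 8.3.1 a positive drug screen goes to the site physician, and dosing may be delayed, the session rescheduled or the participant withdrawn, subject to Medical Monitor review. Section 12.2 also leaves non-compliance to judgment. This stands in part: one cannot say that the protocol is silent on what happens before dosing. But the route is case by case and does not settle whether the use was permitted. The documents also do not say whether the screen covers these opiates.

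It can also be said that 4.3 refers to Section 12.0, so the approver in 12.2 can be read into it, and that the permission in 4.3 might refer to the dose-reduction lead-up. The nearer antecedent is the 12 h/24 h interval, and no precedence is stated. Nor do the 12.x sections simply elaborate 4.3: for other prescription drugs, 4.3 gives one week before the session and 12.3 gives five half-lives.

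A third reply is that unapproved post-dose use will be uncommon. Main-protocol participants remain on site overnight until after the next morning's Integrative Session, with the therapy team or site physician reachable. That stands. Case (b) is mainly residual, for example in the Appendix A sub-study, and case (a) is the firm part.

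Some stronger readings are tempting but not supported:
- **Exclusion 23.** A reader might infer that such use meets the criterion "Require use of concomitant medications that prolong the QT/QTc interval during Experimental Sessions". That criterion concerns participants who need such drugs and refers to Section 12.0, which allows these opiates.
- **QT co-exposure.** A reader might rely on "Opiate medications may reduce the efficacy of MDMA and may prolong QT/QTc interval". The same sentence goes on to say that the allowed opiates were chosen as those with the least such potential.
- **Participant's sole discretion.** Section 4.3 names no approver, but it does not say that the participant alone decides.

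**Conclusion.** The contradiction is real and limited. It covers opiate use in the 12 pre-dose hours and unapproved use in the 24 hours after dosing, at each of three sessions, for participants on an allowed opiate. It does not cover the whole 36 hours (12 + 24), because approved post-session use satisfies both texts.

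The statistical effect is indirect and probably small. It depends on a flare-up occurring inside the interval, on which section the site applies, and on a discretionary withdrawal. The Per Protocol definition in SAP 8.1 has no concomitant-medication test. It is also unclear that the SAP 8.3 category for excluded concomitant treatment fits an allowed drug taken at a restricted time, which adds to the scope for inconsistent coding. The documents do not give the number of opiate users or the frequency of flare-ups. A reader might infer a count of affected sessions by assuming a share of users, but nothing in the documents supports such a share, and not every session of every user would involve a flare-up.

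The conclusion rests on reading the permission in 4.3 as applying to the 12 h/24 h interval. The point deserves correction because the text as it stands cannot be followed consistently on drug exposure around dosing, and the correction is cheap.

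**What to change.** Reconcile Protocol 4.3 and 12.2 to one rule with one set of exceptions and one approver, stated once and cross-referenced from the other section. Align it with the pre-dose medication review in 8.3.1, so that the dosing-day check and Section 12 test the same requirement. Specify which SAP 8.3 category records a departure, and use it at every site. Which exception applies, if any, is for the sponsor and Medical Monitor; this review takes no position.

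The cost is one amended sentence in 4.3 or 12.2, a line on deviation coding and a memo to sites. The downside is that a few sessions may be handled differently from what one of the present texts would have allowed.

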5.0 Protocol Design

5.1 Study Design Overview

This multi-site, randomized, double-blind study assesses the efficacy and safety of MDMA-assisted psychotherapy versus psychotherapy with placebo control in participants diagnosed with at least severe PTSD.

The study will be conducted in N≈100 participants, randomized with a 1:1 allocation to Group 1: MDMA-assisted psychotherapy or Group 2: placebo with psychotherapy. The design includes a planned interim analysis for sample size re-estimation by an independent Data Monitoring Committee (DMC) after 100 participants are enrolled and at least 60% of participants have completed their final CAPS-5 assessment and terminated treatment. There will be separate open-label lead-in protocols following identical study procedures for new therapy teams to receive clinical supervision from the sponsor.

For each participant, the study will consist of:

- **Screening Period:** phone screen, informed consent, eligibility assessment, and enrollment of eligible participants
- **Preparatory Period with Enrollment Confirmation:** medication tapering, Preparatory Sessions and Baseline assessments leading to Enrollment Confirmation
- **Treatment Period:** three monthly Experimental Sessions and associated Integrative Sessions over ~12 weeks plus two CAPS-5 assessments
- **Follow-up Period and Study Termination:** 4 weeks with no study visits, followed by Primary Outcome CAPS-5 and Study Termination visit
- **Invitation to participate in Long-term Follow-up (LTFU) extension study:** 12 months after last Experimental Session

The treatment consists of a flexible dose of MDMA or placebo, followed by a supplemental half-dose unless contraindicated, administered with manualized psychotherapy in three blinded monthly Experimental Sessions. This ~12-week Treatment Period is preceded by three

Preparatory Sessions. During the Treatment Period, each Experimental Session is followed by three Integrative Sessions of non-drug psychotherapy. Experimental Sessions are followed by an overnight stay; a sub-study ([Appendix A](#)) will assess feasibility of Experimental Sessions without an overnight stay. The Primary Outcome measure, the change in CAPS-5 from Baseline (Visit 3), is assessed by a centralized IR pool at 18 weeks post Baseline (Visit 19). The CAPS-5 is also administered as an exploratory measure after Treatments 1 and 2 (Visits 8 and 13). The IR pool will be blinded to treatment assignment, visit number, and number of treatments received, and will not have access to data collected by the sites during the active Treatment Period.

Upon unblinding after database lock, all participants who were assigned to placebo (regardless of CAPS-5 scores), completed the study, meet criteria, and are in good standing with the clinical site will be offered the opportunity to enroll in an open-label safety extension study of manualized MDMA-assisted psychotherapy.

Figure 1: Study Structure Overview

[figure not shown]

Table 1: Study Design Overview

Screening Period From Consent to Enrollment (Visit 0): ~4 weeks (± 2 weeks)			
Study Visit	Visit Duration/ Visit Timing	Brief Description of Events	
Screening	Screening	Multiple visits over 7 to 28 days/ After phone screen/	At initial visit, obtain Informed Consent and assess all screening measures (including PCL-5, Lifetime C-SSRS), medical history, and pre-study medications. Contact outside providers and order medical records, physical exam, labs (including pregnancy and drug tests), ECG, and 1-minute rhythm strip. Once all results and records are obtained, review along with notes from all screening visits and measures. If eligible, send results of LEC-5 & SCID-5-SPQ to IR. Screening may take place over 7 to 28 days at multiple visits.
	Independent Rater Screening	1 hour/ 2 to 9 days after initial eligibility established during Screening	After PCL-5 and initial eligibility are reviewed, an IR will conduct the Since Last Visit C-SSRS, SCID-5-PD, DDIS, and MINI via telemedicine. Results will be confirmed by clinical observation during the Preparatory Period, but the SCID-5-PD, DDIS, and MINI will not be repeated.
Enrollment	Enrollment (Visit 0)	1.5 hours/ 2 to 14 days after Independent Rater Screening	Prior to enrolling: review all screening measures, medical history, discussion with outside providers and sponsor, and any clarification phone calls with participant. Visit is 1.5 hours to review eligibility and medical tapering plan. If enrolled, begin taper, (5 half-lives plus 7 days for stabilization prior to V3). Adverse Event (AE) collection begins.

Preparatory Period with Enrollment Confirmation From Preparatory Session 1 (Visit 1) to Preparatory Session 3 (Visit 4): ~6 weeks (+5/-5 weeks)			
Study Visit/ Visit #	Visit Duration/ Visit Timing	Brief Description of Events	
Preparatory Period	Preparatory Session 1 (Visit 1)	1.5 hours/ 0 to 12 days after Enrollment (V0)	90-minute Preparatory Session. Target visit timing on tapering needs. If needed, schedule calls between Visits 1 and 2 if indicated for tapering, safety, or further questions about medical history.
	Preparatory Session 2 (Visit 2)	1.5 hours/ 2 to 21 days after V1	90-minute Preparatory Session/ongoing assessment. If tapering is complete or not needed, check eligibility and schedule Visits 3 and 4. If tapering is ongoing, schedule post taper call for ongoing assessment.
	Phone Call End Taper	1 hour/ 0 to 7 days after taper and stabilization end; up to 56 days after V0; prior to V3	If needed, confirm medication taper and stabilization is complete and participant is eligible for Baseline CAPS-5. Schedule Visits 3 and 4.
Baseline & Enrollment Confirmation	Baseline CAPS-5 T1 (Visit 3)	1.5 hours/ Post V2 & Medication Taper; before V4	CAPS-5, SDS, and DSP-I completed by an IR via telemedicine after taper is complete. CAPS scores sent ASAP to the therapy team/PI. Due to possibilities of negative side effects of withdrawal from psychiatric medications, the Baseline CAPS-5 should be scheduled as close to the end of tapering as clinically appropriate so that participants who do not meet eligibility criteria can resume their previously prescribed medications as quickly as required for symptom management and participants who do meet criteria can be enrolled and treated as quickly as possible.
	Preparatory Session 3 & Enrollment Confirmation (Visit 4)	3 hours (90-minute measures, 90-minute therapy)/ 3 to 6 days after V3; 1 to 4 days prior to V5	Prior to visit, ensure CAPS-5 confirms PTSD diagnosis and Total Severity Score of ≥ 35 and confirm enrollment by reassessing eligibility criteria. Complete Baseline self-report measures. Complete 3-hour Preparatory Session (~90-minute measures, 90-minute therapy) and schedule Visit 5. If enrollment is not confirmed, do not randomize; complete Study Termination.

Treatment Period From Randomization to Integrative Session 3.3 (Visit 18): 12 weeks (-3/+4)			
Study Visit/ Visit #		Visit Duration/ Visit Timing	Brief Description of Events
Treatment 1	Randomization	.5 hours/ 24 to 48 hours before V5	Complete after enrollment and scheduling Visit 5. Enter demographics in Medrio for use in randomization. The participant does not need to be present for this.
	Experimental Session 1 (Visit 5)	8 hours + overnight/ 4 to 7 days after V3; 1 to 4 days after V4	First Experimental Session is within 2 weeks of the Baseline CAPS-5 (Visit 3), it lasts 8 hours with overnight stay. Dose is 80 mg with supplemental half-dose of 40 mg unless contraindicated.
	Integrative Session 1.1 (Visit 6)	1.5 hours/ Morning after V5	Visit 6 is a 90-minute Integrative Session the morning after Visit 5. Followed by phone check-ins on Days 2, 4, 6, 7, 8, 10, 12, 14 post Visit 5.
	Integrative Session 1.2 (Visit 7)	1.5 hours/ 3 to 14 days after V5; at least 2 days after V6	Between 3 and 14 days after Visit 5, a 90-minute Integrative Session (Visit 7) is completed.
	CAPS-5 T2 (Visit 8)	1 hour 18 to 30 days after V5; between V7 and V9 (may be on same day as either)	Between Visits 7 and 9 (may be same day as either), CAPS-5, SDS, and DSP-I assessment completed by an IR via telemedicine.
	Integrative Session 1.3 (Visit 9)	1.5 hours/ 20 to 34 days after V5; at least 2 days after V7; 1 to 7 days before V10	90-minute Integrative Session post Visit 8 and in preparation for Visit 10. Can occur 1 to 7 days before Visit 10. Measures include LEC-5 and C-SSRS.
	Experimental Session 2 (Visit 10)	8 hours + overnight/ 21 to 35 days after V5	21 to 35 days after Visit 5. The second Experimental Session lasts 8 hours with an overnight stay. Dose is 80 or 120 mg plus supplemental half-dose unless contraindicated.
	Integrative Session 2.1 (Visit 11)	1.5 hours/ Morning after V10	Visit 11 is a 90-minute Integrative Session the morning after Visit 10. Followed by phone check-ins on Days 2, 4, 6, 7, 8, 10, 12, 14 post Visit 10.
	Integrative Session 2.2 (Visit 12)	1.5 hours/ 3 to 14 days after V10; at least 2 days after V11	Between 3 and 14 days after Visit 10, a 90-minute Integrative Session (Visit 12) is completed.
	CAPS-5 T3 (Visit 13)	1 hour/ 18 to 30 days after V10; between V12 and V14 (may be on same day as either)	Between Visits 12 and 14 (may be on same day as either), CAPS-5, SDS, and DSP-I assessment completed by an IR via telemedicine.
Treatment 2	Integrative Session 2.3 (Visit 14)	1.5 hours/ 20 to 34 days after V10; at least 2 days after Integrative Session 2.2 (V12) 1 to 7 days before V15	90-minute Integrative Session post Visit 13 and in preparation for Visit 15. Can occur 1 to 7 days before Visit 15. Measures include LEC-5 and C-SSRS.

Study Visit/ Visit #	Visit Duration/ Visit Timing	Brief Description of Events	
Treatment 3	Experimental Session 3 (Visit 15)	8 hours + overnight/ 21 to 35 days after V10 21 to 35 days after V10 21 to 35 days after V10 21 to 35 days after V10	21 to 35 days after Visit 10. The third Experimental Session lasts 8 hours with an overnight stay. Dose is 80 or 120 mg plus supplemental half-dose unless contraindicated.
	Integrative Session 3.1 (Visit 16)	1.5 hours/ Morning after V15	Visit 16 is a 90-minute Integrative Session the morning after Visit 15. Followed by phone check-ins that includes Since Last Visit C-SSRS assessment on Days 2, 4, 6, 7, 8, 10, 12, 14 post Visit 15.
	Integrative Session 3.2 (Visit 17)	1.5 hours/ 3 to 14 days after V15; at least 2 days after V16	Between 3 and 14 days after V15, a 90-minute Integrative Session (Visit 17) is completed.
	Integrative Session 3.3 (Visit 18)	1.5 hours/ 21 to 35 days after V15	90-minute Integrative Session post Visit 17, 21 to 35 days after Visit 15. Measures include LEC-5 and C-SSRS.

Follow-up Period and Study Termination			
From Integrative Session 3.3 (Visit 18) until Study Termination (Visit 20): 4 weeks (± 2). After Integrative Session 3.3 (Visit 18), ~ 4 weeks with no scheduled study visits until the Primary Outcome is completed.			
Study Visit/ Visit #	Visit Duration/ Visit Timing	Brief Description of Events	
Primary Outcome	Primary Outcome CAPS-5 T4 (Visit 19)	1 hour/ 18 (± 3) weeks (105 to 147 days) after V3; 8 (± 2) weeks (42 to 70 days) after V15	Occurs 105 to 147 days of Baseline and 42 to 70 days) after Experimental Session 3 (Visit 15), Primary Outcome CAPS-5, SDS, and DSP-I assessment completed by an IR via telemedicine. Although there are allowable windows for all visits throughout the protocol, this visit is targeted to be completed within the overall window. Other visits should be scheduled to ensure the timing of the Primary Outcome CAPS-5 T4 assessment is appropriate. In the case of study interruption, Visit 19 should be scheduled 42 to 70 days after Visit 15.
Study Termination	Study Termination (Visit 20)	2 hours ~18 (± 3) weeks (105 to 147 days) after V3; 1 to 9 days after V19	Occurs 105 to 147 days post Baseline and within 1 to 9 days of Visit 19. Complete self-reported and safety measures; create an exit plan for participant. Invite participant to the extension study for LTFU. Let participant who completed the protocol know how they will be informed of unblinding and at that time, if in the placebo group, regardless of CAPS-5 scores, they will be offered the opportunity to enroll at no cost in an open-label safety extension study.

Qualified, blinded IRs selected based on availability from the IR Pool will perform the CAPS-5 assessments as described in table below.

Table 2: Primary Outcome (CAPS-5) Data Collection by Visit

CAPS Number	Visit	Description/Timing	Target Timing Post Baseline (V3)
Baseline CAPS-5 T1	V3	Baseline Between Visits 2 and 4 Preparatory Sessions	0 days
CAPS-5 T2	V8	Post Experimental Session 1 (~3 weeks) Between Visits 7 and 9 Integrative Sessions	~6 weeks
CAPS-5 T3	V13	Post Experimental Session 2 (~3 weeks) Between Visits 12 and 14 Integrative Sessions	~10 weeks
Primary Outcome CAPS-5 T4	V19	Post Experimental Session 3 (~8 weeks)	~18 weeks

